7.4 Statistical Analysis of Analysis Sets

The safety analysis set will serve as the principal data analysis set for the safety.

The PP analysis set will serve as the principal analysis set for the efficacy analyses.

The primary and secondary efficacy assessments will also be performed on the ITD analysis set.

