9.6.6 Secondary Efficacy Analyses

1. The ability of the algorithm, developed under the Exalenz training study IDE# G080227), to identify patients at risk for decompensation at 6 months will be validated using data from Conatus' IND-6556-17 study for the placebo treatment arm.
2. Assessment of the ability of the MBT to predict Clinical Outcome (event free survival versus various deterioration events) at 6 months and at least at 48 weeks and at final treatment visit captured under protocol IND-6556-17 for the emricasan treatment arms.
3. The ability of the ¹³C-methacetin breath test (MBT) to measure the effect of emricasan on the metabolic capacity of the liver at 24 week intervals of treatment and at the final treatment visit versus placebo treated subjects, will be assessed by comparing the differences between the MBT results at each of the 24 - week interval visits and at the final treatment visit versus baseline in all subjects with and without treatment (emricasan) for nonalcoholic steatohepatitis (NASH). This will be done for each of the 3 treatment groups (5mg, 25mg and placebo) separately.

Exalenz Bioscience Ltd.	Last update: May 24, 2017
Study Title: Companion protocol for the ¹³ C-Methacetin Breath Test using the BreathID® MCS System for Conatus phase 2 study of Emricasan, an Oral Caspase Inhibitor, under protocol IDN-6556-17 (IND111463)	Protocol: CON-EX-0217 Version: 2.0
Document Nº: CSP000001	Page 23 of 28

Treatment comparisons will be conducted using a linear mixed-effects model using treatment (3 levels), visit, treatment-by-visit interaction, presence of prior variceal hemorrhage, and presence of prior SBP as fixed effects. The unstructured covariance model will be used. These models will use all available information from all subjects randomized and assume that all missing data is missing at random. Least-square adjusted means (LSMeans) at each visit and the estimated difference and associated 95% CIs between each of the emricasan treatment groups and the placebo group. The LSMeans difference will be tested for each emricasan treatment group versus the placebo group at specified time points.

9.6.7 *Interim Analysis*

9.6.8 *No interim analysis is planned for this study. Pooling*

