3.1.3 Exploratory Objective

- To validate the ability of the MBT to predict specific types of hepatic decompensation events (for each of the two predefined cut-offs independently).
- To describe the change in MBT between the emricasan treatment arms and the placebo arm, thus assessing the response to treatment.

Exalenz Bioscience Ltd.	Last update: August 8, 2019
SAP for Protocol CON-EX-0217: Companion protocol for the ¹³C-Methacetin Breath Test using the BreathID® MCS System for Conatus phase 2 study of Emricasan, an Oral Caspase Inhibitor, under protocol IDN-6556-17 (IND111463)	Document Version: 1.0
Document N°: CSD00109	Page 7 of 21

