7 ANALYSIS SETS

7.1 *Safety Analysis Set*

The Safety analysis set will include all subjects (randomized and non-randomized into the Conatus emricasan study under protocol IDN-6556-17) that initiated at least one MBT (had taken Methacetin), even if the MBT was not completed or the result was not valid.

7.2 *Intent To Diagnose (ITD) Analysis Set*

The intent to diagnose (ITD) analysis set will include all subjects that were randomized into the Conatus emricasan study under protocol IDN-6556-17 and that had at least one valid MBT result.

7.3 *Per Protocol (PP) Analysis Set*

The per protocol (PP) analysis set will include all subjects from the ITD analysis set who did not have any major protocol deviations and exclude any subject that had a previous transjugular intrahepatic shunt (TIPS) or bariatric surgery that may affect the efficacy of the breath test.

Exalenz Bioscience Ltd.	Last update: August 8, 2019
SAP for Protocol CON-EX-0217: Companion protocol for the ¹³C-Methacetin Breath Test using the BreathID® MCS System for Conatus phase 2 study of Emricasan, an Oral Caspase Inhibitor, under protocol IDN-6556-17 (IND111463)	Document Version: 1.0
Document N°: CSD00109	Page 11 of 21

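### The by-arm summary of change in breath test result is planned on the per-protocol set alone, although the protocol specified a model using all randomised subjects

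*SAP*

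**What the plan says.** SAP 7.4 names the sets for efficacy in two sentences: "The PP analysis set will serve as the principal analysis set for the efficacy analyses", followed by "The primary and secondary efficacy assessments will also be performed on the ITD analysis set". Exploratory analyses appear only under the first.

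The sets are defined in SAP 7.2 and 7.3. The intent-to-diagnose (ITD) set is "all subjects that were randomized into the Conatus emricasan study under protocol IDN-6556-17 and that had at least one valid MBT result". PP is "all subjects from the ITD analysis set who did not have any major protocol deviations", and it must also "exclude any subject that had a previous transjugular intrahepatic shunt (TIPS) or bariatric surgery that may affect the efficacy of the breath test". Section 7.3 does not say what counts as a major deviation, and it does not limit deviations to those before randomisation or to those affecting the breath test.

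The SAP places MBT change by arm among the exploratory objectives (3.1.3): "To describe the change in MBT between the emricasan treatment arms and the placebo arm, thus assessing the response to treatment". Section 8.4.3.2 plans descriptive summaries of change and percent change in PDR peak and in cPDR at 30 minutes for each treatment group, with no statistical test.

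In the protocol the same question is secondary. Section 9.6.6 item 3 specifies a linear mixed-effects model testing each emricasan arm against placebo, and says of its population: "These models will use all available information from all subjects randomized and assume that all missing data is missing at random". SAP section 2 gives the SAP precedence where the two documents differ.

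**The concern.** For the prognostic question (does a low PDR peak predict decompensation?), a PP set that removes people in whom the breath test may not work has a rationale, and an ITD run accompanies it. The by-arm MBT change is a different kind of question. It sets randomised groups side by side in order to judge response to treatment, and its validity rests on the groups staying as randomised. Removing subjects for deviations that arise during treatment can undo that if the deviations differ by arm and go with liver function. A table of means is distorted by such exclusions just as a tested difference is.

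When the SAP moved this analysis from secondary to exploratory, it also fell outside the sentence that would have given it an ITD run. Section 8.4.3.2 explains the absence of a test by the small expected sample. That does not explain the narrower population, and a small sample is a reason against further exclusions.

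**Working it through.** There is no planned figure to reproduce. The documents give no effect size, SD, power or PP exclusion rate for this endpoint, so the check is mainly textual.

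**Step 1: which set applies.**
- SAP 7.4: PP for all efficacy; ITD in addition for primary and secondary only.
- SAP 3.1.3, 3.2.3 and 8.4.3.2: MBT change by arm is exploratory.
- Result: PP only.

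**Step 2: what changed from the protocol.**
- Status: secondary (protocol 9.6.6 item 3) to exploratory (SAP 3.1.3).
- Method: mixed model with tests to descriptive summary. Reason given: small sample.
- Population: all available data from randomised subjects to PP. No reason given.

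**Step 3: planned numbers.** Inputs from SAP 4.1: 70 per arm in three arms, and about 90% performing the MBT.
- Randomised: 3 × 70 = 210.
- With an MBT: 0.9 × 210 = 189, or 63 per arm. This approximates the planned ITD set; the actual set may be smaller, since SAP 4.1 allows as few as 120 MBT results at screening.
- PP at assumed exclusion shares, equal across arms:

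| Assumed share excluded | PP total | Per arm | Share of 210 |
|---|---|---|---|
| 5% | 189 × 0.95 ≈ 180 | about 60 | 86% |
| 10% | 189 × 0.90 ≈ 170 | about 57 | 81% |
| 20% | 189 × 0.80 ≈ 151 | about 50 | 72% |

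These are before the loss of subjects without a follow-up MBT. At 20%, with an unchanged SD, the standard error of an arm mean rises by √(63/50) = 1.12.

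**Step 4: how exclusion moves a mean.** Take one arm and its subjects with paired MBTs. Let p be the share excluded from PP, R the mean change in those retained and X the mean change in those excluded.
- Mean before exclusion = (1 − p)R + pX; PP mean = R.
- PP mean minus mean before exclusion = p(R − X).
- If d = R − X is the same in both arms, the emricasan-minus-placebo difference shifts by (p_emricasan − p_placebo) × d.

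Illustration, with every input assumed: p = 5% on placebo and 10–20% on an emricasan arm; d = 1–2 %/h on PDR peak.
- Low: (0.10 − 0.05) × 1 = 0.05 %/h.
- High: (0.20 − 0.05) × 2 = 0.30 %/h.

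With equal shares and equal d the shift is zero. If placebo loses more subjects, the sign reverses.

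**Step 5: would the plan show it?** SAP 8.3 reports, by treatment group, PP exclusions by reason and valid MBTs per visit. That shows p in each arm. It does not show R − X, so the effect on MBT change stays unseen without a second summary.

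**The case against.** The strongest reply is that this is an untested exploratory table in a study about prognosis, and that the plan already contains safeguards. Much of that is right, and it limits what can be claimed.

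- A reader might infer that this is the SAP's only contrast between arms. It is not. The primary Cox model (8.4.1) includes randomised arm, reports a hazard ratio, interval and p-value for each covariate, and is run on PP and ITD. That is an adjustment step for time to event, however, and says nothing about MBT change.
- A reader might infer that differential exclusion would go unnoticed. SAP 8.3 contradicts this for the counts, though not for their effect on the means.
- A reader might infer that no result on all randomised subjects will exist anywhere. Protocol 9.1 makes MBT response to emricasan a secondary goal of the main study, whose analysis set is not in these documents. The claim is limited to this SAP.
- The protocol's own population was not cleanly all-randomised. Protocol 9.5 requires valid MBT measurements for efficacy, and 9.6.9 leaves out subjects without MBT results. That stands, but neither section removes subjects for deviations during the study in the way SAP 7.3 does.
- The main study is double-blind, which makes arm-dependent deviations less likely without excluding them. Previous TIPS and bariatric surgery read as history and are not the problem here.
- A reader might infer that the mortality and transplant analyses in SAP 8.4.3.1 also lack an ITD run. They are to be done much as the primary analysis is, which may already imply both sets, and they concern prognosis and not a comparison of arms.

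**Conclusion.** The point holds in a limited form. As SAP 7.4 is written, its only description of MBT response to emricasan versus placebo rests on a set from which subjects can be removed for events after randomisation, with no ITD version beside it and no reason given for the change of population.

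The documents do not support reading this as a threat to a treatment-effect claim. No test or confidence interval is planned for the endpoint, so there is no type I error at stake; what can be wrong is the description. The documents also do not show that any bias exists. The 0.05–0.30 %/h range rests wholly on assumed exclusion shares and an assumed difference between retained and excluded subjects, and its direction is unknown. This is a modest weakness, worth correcting because the correction is almost free.

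**What to change.** Add to SAP 7.4: *The MBT change summaries (8.4.3.2) will be presented by randomised arm for all ITD subjects with a valid baseline MBT and a valid MBT at the visit concerned, and also on the PP set.* Leave the ITD definition in 7.2 as it is. This summary still depends on having a follow-up MBT, so it will not be an all-randomised result, but it removes exclusion for deviations.

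Beside it, report per arm the number randomised, the number with paired MBTs at each visit, and the number excluded from PP by reason; 8.3 already supplies the last of these. State in the SAP, or in the clinical study report if the SAP is closed, why the population and method of protocol 9.6.6 item 3 were not kept.

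Optionally, say in 7.4 that the 8.4.3.1 analyses are also run on ITD.

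The cost is a few lines of text and a second run of existing summary programs. No new data are needed.

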8 STATISTICAL ANALYSES

8.1 General Considerations for Data Analyses

All analyses will be performed using either SAS® v9.4 or higher (SAS Institute, Cary NC, US) or the R software version 3.6 or higher (R Development Core Team. Vienna, Austria).

The standard summary statistics for continuous variables are: N, mean, standard deviation, median, minimum and maximum. The standard summary statistics for categorical variables are: count and proportion.

Any statistical tests performed, will be two-sided. The required significance level of findings will be equal to or lower than 5%. Where confidence limits are appropriate, the confidence level will be 95%. Nominal p-values and unadjusted confidence intervals will be presented.

8.2 Baseline Definitions

The study baseline will be defined as the last available, non-missing observation prior to first study drug (emricasan or placebo) administration, unless specifically mentioned otherwise.

For survival models: The first valid MBT test will be defined as the baseline and day 0 of follow up. For MELD scores, the first value measured on or after the day of the first valid MBT will serve as baseline value, even if there are later MELD results available prior to first study drug (emricasan or placebo) administration. The MELD progression outcome, 4 point increase in MELD, will thus be calculated by comparing each MELD score to the first available MELD score on or after the first valid MBT date.

Exalenz Bioscience Ltd.	Last update: August 8, 2019
SAP for Protocol CON-EX-0217: Companion protocol for the ¹³C-Methacetin Breath Test using the BreathID® MCS System for Conatus phase 2 study of Emricasan, an Oral Caspase Inhibitor, under protocol IDN-6556-17 (IND111463)	Document Version: 1.0
Document N°: CSD00109	Page 12 of 21

8.3 Disposition of Patients

Subject dispositions will be summarized based on all subjects screened into the study, and for each treatment group.

The following subject disposition information will be presented:

- The number and percentage of subjects who had valid MBT for each visit.
- The number and percentage of reasons for not having a valid MBT for each visit.
- The number and percentages of subjects that were excluded from the PP analysis set, by reason for exclusion.

8.4 Efficacy Analyses

All hepatic decompensation events will be summarized descriptively in summary tables for each event type described in the following sections.

8.4.1 Primary Endpoint

The MBT parameter used to predict hepatic decompensation event is PDR_{peak}. Any PDR_{peak} value of less or equal to 5.5 %/h (see **Appendix A** for detailed description of parameter calculation) will be considered as ‘high risk’ and any value above that threshold will be considered as ‘lesser risk’. The dichotomous MBT result will be tested for significance using the Cox proportional hazards regression model with site and Conatus protocol IDN-6556-17 randomized arm as covariates. If the Conatus protocol IDN-6556-17 randomized arm factor is found non-significant (i.e. p-value > 0.05), then this factor will not be a covariate for the main analysis to be performed. If the Conatus protocol IDN-6556-17 randomized arm factor is found statistically significant (i.e. p-value ≤ 0.05), then the main analysis will be performed keeping this factor as a covariate (to ‘adjust’ the analysis for treatment).

The following list defines the hepatic decompensation events for the primary endpoint:

- Liver-specific mortality
- Liver transplant
- New and/or recurrent hepatic decompensation events

Exalenz Bioscience Ltd.	Last update: August 8, 2019
SAP for Protocol CON-EX-0217: Companion protocol for the ¹³C-Methacetin Breath Test using the BreathID® MCS System for Conatus phase 2 study of Emricasan, an Oral Caspase Inhibitor, under protocol IDN-6556-17 (IND111463)	Document Version: 1.0
Document N°: CSD00109	Page 13 of 21

- Variceal hemorrhage that required ‘non-drug therapy’ (e.g. variceal ligation, sclerotherapy) based on the AE log or requiring hospitalization
- Portal hypertensive gastropathy hemorrhage requiring hospitalization
- Occurrence of large gastroesophageal varices or any varices with red wale sign (classified as severe in the AE log) and that required ‘non-drug therapy’ (e.g. variceal ligation or sclerotherapy) based on the AE log to avoid hemorrhage
- Ascites requiring diuretics (in a subject without prior history of ascites requiring diuretics) or refractory ascites requiring ‘non-drug therapy’ (e.g. paracentesis) based on the AE log (in a subject with history of ascites requiring diuretics).
- Any onset of hepatic encephalopathy (HE) requiring hospitalization (classified as SAE) in the absence of known co-morbidities or alternative causes.
- Hepatorenal syndrome requiring hospitalization
- Spontaneous bacterial peritonitis (SBP) requiring hospitalization
- MELD score progression defined as any increase ≥ 4 points from baseline

These hepatic decompensation events are identified using the study’s ‘new decompensation event’ dataset as well as events listed in the AE and SAE logs, the reason for (early) termination, the comment and the lab results (incl. MELD scores) datasets. All potential hepatic decompensation events will be adjudicated through a medical review prior to the primary efficacy analysis and blinded to the breath test results. Once defined and adjudicated, the first of the hepatic decompensation events after the first valid MBT will be used for the respective event-free survival analysis.

All MELD scores will be calculated using the formula from the US Organ Procurement and Transplantation Network (OPTN) Policy from 2016 (**Appendix B**). MELD score progression will not include subjects who are started on anticoagulants after the first valid

Exalenz Bioscience Ltd.	Last update: August 8, 2019
SAP for Protocol CON-EX-0217: Companion protocol for the ¹³C-Methacetin Breath Test using the BreathID® MCS System for Conatus phase 2 study of Emricasan, an Oral Caspase Inhibitor, under protocol IDN-6556-17 (IND111463)	Document Version: 1.0
Document N°: CSD00109	Page 14 of 21

MBT (and prior to the identified MELD progression event) that can affect the PT or INR at the time of MELD assessment.

The time-to-first event will be derived as the number of days between the day of the screening MBT test and the date when the first hepatic decompensation event occurs or when a subject is censored (i.e., event/censored date minus screening MBT date plus 1). Subjects will be censored at their last study visit for the following reasons:

- If a subject discontinues the study prior to the end of the study without experiencing a hepatic decompensation event
- If a subject reaches the Final Treatment visit without experiencing a hepatic decompensation event
- If a subject develops hepatocellular carcinoma (HCC)

Survival analysis will be conducted using the Cox proportional hazard model. The model summary will include the number of subjects in the model, and a table with each covariate in a separate line specifying the coefficient's value, Hazard Ratio, Hazard Ratio 95% Confidence Interval and p-value. In addition, a Kaplan-Meier plot for event-free survival will be presented, stratified by MBT parameter along with the MBT parameter log-rank p-value. Additionally a crosstab table of MBT parameter and events will be presented.

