4.1 Sample Size Considerations

The plan is to enroll a subset of subjects that will be screened under Conatus' IDN-6556-17 study. This Conatus study plans to enroll 210 subjects (70 subjects per treatment arm) to be randomly assigned to 1 of 3 treatment groups, 2 doses of emricasan (25 mg or 5 mg) or placebo in a 1:1:1 ratio. A 45% screen failure (SF) rate is estimated. It is expected that approximately 90% of the patients enrolled will perform the MBT. The total number of MBT results expected ranges between 120 and 310 at screening and up to 200 at respective study visits with 24-week intervals and at the final treatment visit.

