6 SIGNIFICANCE LEVELS AND HANDLING OF TYPE I ERROR

6.1 Type I Error

The overall significance level for this study is 5% using two-tailed tests, except for treatment by site interaction that will be tested at a significance level of 10%.

Exalenz Bioscience Ltd.	Last update: August 8, 2019
SAP for Protocol CON-EX-0217: Companion protocol for the ¹³C-Methacetin Breath Test using the BreathID® MCS System for Conatus phase 2 study of Emricasan, an Oral Caspase Inhibitor, under protocol IDN-6556-17 (IND111463)	Document Version: 1.0
Document N°: CSD00109	Page 10 of 21

6.2 *Hierarchy Approach for Secondary Endpoint Analysis*

The hierarchy approach will be adopted for the primary and secondary endpoints to control type I error due to multiple endpoint testing. Thus the primary endpoint will first be analyzed and only if $p < 0.05$, will the secondary endpoint be analyzed. This approach will maintain the overall study type I error by continuing to analyze the next end-point in the hierarchy only if the previous endpoint analysis was found significant. The hierarchy approach is extended for the secondary endpoints as well, according to the order that they appear in section 3.2.2 above.

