8.4.2 Secondary Endpoints

8.4.2.1 The overall event-free survival with a second predefined cut-off

The event free survival will be analyzed in the same manner as the primary endpoint analysis with the exception that the dichotomous MBT result will be based on a second predefined cut-off: Any PDR_{peak} value of less or equal to 7.5 %/h (see **Appendix A** for detailed description of parameter calculation) will be considered as 'high risk' and any value above that threshold will be considered as 'lesser risk'.

Exalenz Bioscience Ltd.	Last update: August 8, 2019
SAP for Protocol CON-EX-0217: Companion protocol for the ¹³C-Methacetin Breath Test using the BreathID® MCS System for Conatus phase 2 study of Emricasan, an Oral Caspase Inhibitor, under protocol IDN-6556-17 (IND111463)	Document Version: 1.0
Document N°: CSD00109	Page 15 of 21

8.4.2.2 *The one-year event-free survival*

The one-year event free survival will be analyzed in the same manner as the primary endpoint analysis with the exception of censoring all subjects after 1 year (365 days) from baseline MBT date.

This analysis will be repeated while using the second pre-defined cut-off described in the first secondary endpoint (section 8.4.2.1).

8.4.2.3 *The event free survival when using all the repetitions of the MBT measurements (time dependent parameter)*

The event free survival will be analyzed in the same manner as the primary endpoint analysis with the exception of using all repetitions of the MBT measurements while dividing the prediction times to the intervals between tests by applying the Time dependent covariate method.

This analysis will be repeated while using the second pre-defined cut-off described in the first secondary endpoint (section 8.4.2.1).

8.4.2.4 *The six-month event-free survival*

The six-month event free survival will be analyzed in the same manner as the primary endpoint analysis with the exception of censoring all subjects after six months (180 days) from baseline MBT date.

This analysis will be repeated while using the second pre-defined cut-off described in the first secondary endpoint (section 8.4.2.1).

8.4.2.5 *The event-free survival considering only new hepatic decompensation events as defined in Conatus study protocol IDN-6556-17*

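### Randomised arm is kept in or dropped from the Cox models by its own p-value: the effect on the primary result is small, but the time-dependent MBT analysis is left open to modest confounding

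*SAP*

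**What the plan says.** SAP 8.4.1 starts from a "Cox proportional hazards regression model with site and Conatus protocol IDN-6556-17 randomized arm as covariates". It then applies a rule: "If the Conatus protocol IDN-6556-17 randomized arm factor is found non-significant (i.e. p-value > 0.05), then this factor will not be a covariate". If the arm p-value is 0.05 or below, "then the main analysis will be performed keeping this factor as a covariate". Arm has three levels, since SAP 4.1 describes "2 doses of emricasan (25 mg or 5 mg) or placebo in a 1:1:1 ratio". The SAP does not say whether the arm p-value is a joint two-degree-of-freedom test or one per dose contrast. It plans no arm-adjusted result for the case where arm is dropped.

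The rule carries forward. SAP 8.4.2.1 says: "The event free survival will be analyzed in the same manner as the primary endpoint analysis". Sections 8.4.2.2 to 8.4.2.5 use the same formula, mostly for both cut-offs, and SAP 7.4 has the primary and secondary efficacy analyses done in the PP and the ITD set. Nothing says that the choice made for the primary model is carried over, so the natural reading is that the arm test is repeated each time.

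The protocol's primary analysis (6.4, 9.2.1, 9.6.5) was confined to placebo. The SAP prevails over the protocol (SAP 2), and its efficacy sets draw on all randomised subjects (SAP 7.2, 7.3). The arm term is therefore its only adjustment for treatment.

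**The concern.** The rule is prespecified, but the model it produces is not: a test on the same outcome data selects it. A p-value above 0.05 does not show that arm has no effect, least of all in a study not sized to test arm in this model. Three things are at stake.

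- **Comparability.** The primary analysis and 8.4.2.1 to 8.4.2.4 make 1 + 1 + 2 + 2 + 2 = 8 models, or 16 over the two analysis sets, each with its own keep-or-drop decision. The six-month models have fewer events and so are more likely to lose arm. HRs could then differ between endpoints partly because the covariates differ.
- **The primary test.** Its p-value opens the testing hierarchy in SAP 6.2, so it matters whether selection distorts it.
- **On-treatment MBT.** In 8.4.2.3 the later breath tests are taken on study drug. The ITD set needs only one valid MBT at any time (SAP 7.2), and SAP 8.2 takes the first valid MBT as survival baseline, so even a baseline test could fall after randomisation. If emricasan both improves MBT and reduces events, arm is a common cause, and leaving it out pushes the MBT HR away from 1, in the direction that favours the test.

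**Working it through.** **Inputs from the documents.** 210 randomised, 70 per arm; "It is expected that approximately 90% of the patients enrolled will perform the MBT", so 0.9 × 210 = 189; at least 120 screening MBT results (SAP 4.1); "The overall significance level for this study is 5% using two-tailed tests" (SAP 6.1). There is no stated power, event count or HR, so no plan figure to reproduce.

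**Assumptions.** Events from 36 (30% of 120) to about 114 (60% of 189). Emricasan HR against placebo from 0.8 to 0.5.

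**Step 1: how often arm is kept.** For a joint two-degree-of-freedom Wald test with three equal arms and E events, the noncentrality is λ = E × V, where V is the variance of the log HRs (0, ln HR₁, ln HR₂) across arms. With one HR for both doses, V = (2/9)(ln HR)². Arm is kept with probability P(χ²₂(λ) > 5.99). At HR 0.7, V = (2/9) × 0.1272 = 0.0283; with 76 events λ = 2.15 and the probability is 24%.

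| Emricasan HR | 36 events | 50 | 76 | 95 | 114 | Events for 50% chance of keeping arm |
|---|---|---|---|---|---|---|
| 0.8 both doses | 8% | 9% | 12% | 14% | 16% | 448 |
| 0.7 both | 13% | 17% | 24% | 29% | 34% | 176 |
| 0.8 and 0.6 | 19% | 24% | 35% | 43% | 50% | 114 |
| 0.6 both | 23% | 31% | 45% | 55% | 63% | 86 |
| 0.5 both | 40% | 53% | 72% | 82% | 89% | 47 |

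The last column needs λ of about 4.96. At HR 0.5, V = (2/9) × 0.4805 = 0.1068, and 47 × 0.1068 = 5.02. With no treatment effect, arm is dropped 95% of the time.

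**Step 2: effect on the primary analysis (MBT before randomisation).** Simulation: 1,500 trials per scenario, 189 subjects, 12 site groups, 40% high risk, exponential event times, follow-up uniform over 0.9 to 1.8 years. Each trial was analysed with arm always kept and by the SAP rule.

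| | Arm HR 1 | 0.7 | 0.5 |
|---|---|---|---|
| Type I error, always keep | 5.5% | 5.1% | 6.7% |
| Type I error, SAP rule | 5.4% | 5.0% | 6.7% |
| Power at MBT HR 2, always keep | 92.9% | 89.5% | 84.0% |
| Power at MBT HR 2, SAP rule | 92.9% | 89.6% | 83.9% |

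Simulation error on the type I figures is about 0.6 points. The 6.7% is the same under both approaches, so it is not due to the rule. With a true MBT HR of 2, the median estimate with arm / without arm / by the rule was 2.08 / 2.06 / 2.07 at arm HR 0.7, and 2.07 / 2.00 / 2.06 at 0.5.

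A second simulation (MBT HR 1.8, no site term) compared the rule directly with always keeping arm. The MBT significance verdict differed in 1.8% of trials at arm HR 0.7 and 1.6% at 0.5. In 5% of trials the two MBT HRs differed by more than 6.3% and 5.7% respectively. A further run gave verdict changes in 2.5% and 0.8%, and gaps of about 6% and 4%.

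**Step 3: effect on 8.4.2.3 (MBT on treatment).** Simulation: 189 subjects, about 63 to 74 events, true MBT HR 1.0, 1,500 runs, no site term, emricasan assumed to cut on-treatment high-risk prevalence from 50% to 20%.

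| | Arm HR 0.7 | Arm HR 0.5 |
|---|---|---|
| Median MBT HR, arm kept | 0.99 | 1.02 |
| Median MBT HR, arm omitted | 1.06 | 1.15 |
| False positives, arm kept | 5.3% | 4.4% |
| False positives, arm omitted | 6.6% | 7.0% |
| False positives, SAP rule | 6.4% | 5.2% |

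With a smaller shift (50% to 35%), the median HR was 1.05-1.06 and false positives were close to nominal. A separate run, also assuming that emricasan improves MBT, gave median MBT HRs under the rule of 1.08 (arm HR 0.7) and 1.04 (arm HR 0.5), against 1.02 and 1.00 with arm kept. The two estimates differed by more than 15-17% in 5% of those runs.

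**The case against.** The best defence is structural. The planned baseline MBT is done at screening (protocol 10.1), before randomisation, so arm is independent of it by design and does not confound the primary comparison. The rule fixes its threshold and consequence in advance and leaves the analyst little discretion. SAP 8.4.1 also requires a table with one line per covariate, so a reader will see whether arm is in the model. All of this stands for the primary analysis, and Step 2 bears it out.

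A reader might infer that selecting the model by p-value inflates the primary type I error and so undermines the hierarchy. The simulations do not support that: the error is the same with the rule as with arm fixed. Nor should the raw gap between models with and without arm be taken as the rule's effect. That gap exceeds 9.3% (arm HR 0.7) or 14.3% (arm HR 0.5) in 5% of trials, but it counts trials in which the rule would have kept arm.

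One could also argue that a purely prognostic question needs no treatment adjustment. That argues for leaving arm out throughout, not for letting its p-value decide, and SAP 8.4.1 itself gives adjustment for treatment as the reason for the term.

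The defence does not reach 8.4.2.3, or any first valid MBT taken after randomisation, because randomisation does not make those results independent of arm.

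**Conclusion.** The point holds as a should-fix item. The covariate set is chosen by the outcome data and may differ across endpoints, cut-offs and analysis sets.

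For the primary analysis with a screening MBT the demonstrated harm is small: slight attenuation, no visible type I inflation, and a different MBT significance verdict from always keeping arm in about 1-3% of simulated trials. For the time-dependent analysis, third among the secondary endpoints in the hierarchy, the rule leaves modest confounding: a median MBT HR of about 1.04-1.08 when the truth is 1.0. That size depends on emricasan markedly improving MBT.

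It is tempting to add that the rule usually omits arm even when treatment works. The documents do not support this without a condition, because they give neither an event count nor a treatment effect. On the assumed 36 to 114 events it is true at HR 0.7 or weaker, and at HR 0.6 below about 86 events. It is false at HR 0.5 with about 47 or more events.

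**What to change.** In SAP 8.4.1, delete the two conditional sentences about the arm p-value. State that randomised arm, as a three-level factor, stays in the primary and every secondary Cox model whatever its p-value, or stratifies the baseline hazard. Say explicitly that this covers 8.4.2.3, both cut-offs, and both the PP and ITD sets. Show the model without arm only as a sensitivity analysis. This also removes the ambiguity over joint or per-dose testing.

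The cost is wording and two degrees of freedom, with no visible loss of power (Step 2). SAP 2 allows amendment until the sponsor accesses the data; after that, the change would be documented as a deviation in the study report.
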